3. Impaired participant performance on the Trail Making Test or Stroop Test (Exclusio n Criterion #5): this will not be re-assessed. Other re-screening questions will be used to inform the study staff of any changes to brain structure/function (i.e., any recent diagnoses regarding neurological/psychological/psychiatric conditions). If the investigator is concerned that the participant may not perform at normative levels on neuropsychological testing, the participant will be invited in for a full re-screening (Visit 1b).

4. Grip strength test performance (Exclusion Criterion #6): this will not be re-assessed. Other rescreening questions will be used to inform the study staff of any changes to brain structure/function (i.e., any recent diagnoses regarding neurological/psychological

/psychiatric conditions) or musculoskeletal health (i.e., any recent diagnoses of musculoskeletal impairments).

Additionally, the obesity criterion (Exclusion Criterion #8) will be assessed based on the anthropometric measure obtained from the participant in his or her initial Visit 1:

a. Participants with BMI < 30: for a participant, whose BMI is below 30, we will ask during the rescreening if he or she has gained weight since the initial study visit. If the answer is yes, the previously measured height of the participant and the self-reported current weight of the participant will be used to calculate BMI. If the participant still falls below a BMI of 35 with his or her new weight, then he or she will still be considered eligible for the study. If the participant falls at or above a BMI of 35, he or she will be invited in for a full re-screening (Visit 1b). This is due to the fact that a BMI of 35 or greater is one of the exclusion criteria to be considered in the obesity criterion (exclusion criterion#8).

b. Participants with $BMI \ge 30$: these participants will be invited in for a full re-screening (Visit 1b).

Procedures for Pilot studies:

For pilot studies involving only fMRI and/or cognitive testing (no neuropsychological assessment, fitness testing, or exercise training), participants will already come in for their initial study visit tentatively scheduled for behavioral testing and/or fMRI on the same day and/or on a day in the near future. However, the study staff will confirm the visit based on 1) whether they are still interested after explanation of the procedures and 2) whether they are eligible to participate based on screening.

Cognitive pilot:

The cognitive pilot requires two visits, which may be combined into a single visit. During the first visit, the investigator will review the consent form with the understanding that their choice to participate is completely voluntary. Following informed consent, the participant will undergo further screening questionnaires to determine eligibility. Visit 1 will last approximately 1 to 1.5 hours. Once fully deemed eligible, the second visit is for cognitive testing. The participant will perform the cognitive tasks on a computer screen. Breaks will be given in between runs as necessary and requested. Visit 2 will last approximately 1 to 2.5 hours.

fMRI pilot:

The fMRI pilot requires two visits, which may be combined into a single visit. During the first visit, the investigator will review the consent form with the participant to convey the understanding that his or her choice to participate is completely voluntary. Following informed consent, the participant will undergo further screening questionnaires to determine eligibility. This will include the CNC Screen Form (item 6, above), which will determine MRI safety for that subject. Visit 1 will last approximately 1 to 1.5 hours. Once fully deemed eligible, the second visit is for fMRI scanning. The participant will perform the cognitive tasks in the scanner. Breaks will be given in between runs as necessary and requested. Visit 2 will last approximately 1 to 2.5 hours. The same MRI procedures as described in study visit 3.

Screening for participants of pilot studies

Participants recruited for pilot studies (behavioral pilot/pilot of cognitive tasks only; fMRI pilot

/pilot of cognitive tasks in fMRI scanner; no neuropsychological testing, no cardio-respiratory fitness evaluation or exercise training) will be asked to fill out the short version of the General Screening Form (item 2, above) and the Edinburgh Handedness Inventory (item 8, above).

Participants recruited for fMRI piloting will additionally be asked to fill out the CNC Screen Form (item 6, above).

Description of functional MRI procedures for fMRI pilot

Before the MRI, we will ask the participant about any metal in or on his or her body. The participant will be asked to remove all metal objects, regardless of whether they are ferromagnetic (e.g. hearing aids, dentures, jewelry, watches, hairpins, and makeup with metallic specs) from his or her body. If the participant's clothing contains non-removable metals, such as metal zippers or buttons, especially near the head (e.g. on t-shirts or sweatshirts), the participant may be asked to put on a hospital gown instead (the MR technologist in charge of the scans will be consulted). During the screening visit we will ask the participant to prepare by wearing metal-free clothing on the day of the MRI exam.

Before entering the MRI scanning room, we may take vital sign measurement and the participant will receive task instructions. At this time, the participant will practice each task. Then, immediately before entering the MRI, we will ask the participants to wear earplugs to reduce the scanner noise.

During the MRI, the participant will be required to lie still on the MRI table. The participant will be able to hear and speak to the research staff at all times during the MRI procedures, but we will ask him or her not to speak during any scans unless there is an emergency (for example, if he or she feels claustrophobic or sick) or he or she is prompted to speak. The researcher and/or the MR technologist will remain in contact with the participant throughout the study, and the participant may terminate his or her participation in the study at any time (even during a scan). We can stop the procedure at any time, if necessary.

When the participant is in the MRI scanner we will begin by taking several structural brain images. Soon after this, the cognitive tasks will begin. We will instruct the participant to look at virtual environments, pictures, words and/or objects while he or she is inside the MRI scanner. S

/he may be asked to listen to words and/or sounds through a headset while s/he is in the scanner. S/he may be moved passively through a virtual environment or s/he may be asked to move actively through a virtual environment using a joystick or button-box. While in the scanner

s/he may be asked to make decisions about the presented stimuli, scenes, or environments, and to indicate responses on handheld response keys or with a joystick. Between each set of stimuli there will be a short break. We will remind the participant to keep his or her head as still as possible during task performance and the breaks in between.

We may take measurements of blood pressure, heart rate and/or pulse immediately before entering and immediately after exiting the fMRI scanner room. During fMRI scanning we may use pulse oximetry.

Outcomes

Describe anticipated primary outcome and any secondary outcomes and how they will be measured:

Primary Outcomes for Specific Aim #1:

1) Better cognitive task performance post-exercise training compared to baseline (measurements: reaction times, accuracy, etc.); effect expected to be greater for aerobic exercise training than control (strength, balance and flexibility training)

Measurements: reaction times, accuracy, and other cognitive task derived scores

2) Increased activation in and functional connectivity between brain areas associated with task performance, effect expected to be greater following aerobic exercise training than control. Measurements: blood-oxygen level dependent fMRI scans

Primary Outcomes for Specific Aim #2:

1) Better cognitive task performance post-exercise training compared to baseline (measurements: reaction times, accuracy, path length, spatial reasoning test scores, etc.); effect expected to be greater for aerobic exercise training than control (strength, balance, and flexibility training)

Measurements: reaction times, accuracy, path length, and other cognitive task derived scores

2) Increased activation in and functional connectivity between brain areas associated with task performance, effect expected to be greater for aerobic exercise training than control; this effect of aerobic exercise training will be greater for subjects with 1) smaller compared to larger relative entorhinal cortex volume, and 2) below-median compared to above median path integration skills

Measurements: blood-oxygen level dependent fMRI scans

Secondary outcomes for all aims:

1) Increased aerobic capacity for aerobic exercise group participants

Measurements: VO2max (estimated from submaximal incremental work rate test)

2) Increased strength for control group participants

Measurements: upper body strength in lbs or kg (based on chest press and latissimus dorsi pulldown), lower body strength in lbs or kg (based on leg press)

3) Increased lean body mass

Measurements: Percent lean body mass from BIA (and/or skinfold measures)

4) Neuropsychological test performance: improved performance scores on tests of spatial cognition, verbal memory, visuo-spatial memory, visuo-spatial attention, and executive functions post-exercise training compared to baseline and compared to controls

Measurements: neuropsychological test scores

Data Analysis

Provide a description of your plan for data analysis. State the types of comparisons you plan (e.g. comparison of means, comparison of proportions, regressions, analysis of variance). Which is the PRIMARY comparison/analysis? How will the analyses proposed relate to the primary purposes of your study? If you are doing qualitative research please state how comparisons will be made.

Specific Aim #1:

Behavioral and Fitness Data Analysis. The primary measures for the primary cognitive task (Sternberg memory load task) are % correct and reaction times, and for fitness are estimated VO 2 max. The primary statistical analyses will be repeated-measures ANOVAs with the factors group (aerobic vs. control) and time (pre vs. post) to examine group x time interactions on the outcome measures. Posthoc tests (e.g. Tukey tests) will examine if a significant group x time interaction is due to a greater improvement post-intervention in the aerobic exercise group compared to controls. Dependent measures will be tested for normality and skewed data log-transformed. We will use an alpha of 0.05, corrected for multiple comparisons.

Univariate fMRI and Functional Connectivity Analyses. We will use SPM8 and related software for statistical analysis of fMRI data. We will estimate voxel-based Statistical Parametric Maps (SPMs)

and compare them between and within groups with mixed-design ANOVAs. We will use baseline fitness as a covariate. Because the entorhinal cortex and the hippocampus are our primary brain regions of interest, we will use a seed-based functional connectivity approach. We will compare task-related functional connectivity: 1) pre versus post intervention, and 2) aerobic exercise versus control. We will use the psycho-physiological interaction (PPI) approach91 using the Generalized PPI Toolbox92 for SPM8. The time course from a seed region constitutes the physiological variable, and the contrast of interest (e.g. high memory load > low memory load) constitutes the psychological variable in the PPI model. Our search space will be restricted to the medial temporal lobe region. We will determine the PPI variable by calculating the voxel-wise product between the physiological and the psychological variables. We will also correlate SPMs and functional connectivity strength with cognitive test scores. Analyses will include nuisance regressors (e.g. head motion).

Specific Aim #2:

Data Analysis. See Aim #1. The behavioral outcome variables of the primary cognitive task (allocentric navigation task) are distance traveled and movement speed. Addicional outcome variables are neuropsychological test scores and spatial reasoning test scores. Analyses will be as described for Specific Aim #1. In addition, we will compare two groups that differ in relative EC volume or path integration ability (by median split) using descriptive statistics (means, confidence intervals) due to the exploratory nature/ small sample size.

Sample Size

Sample Size Justification

Approximately 94 participants will be recruited total for the study: For the exercise training program

/study intervention, approximately 84 participants will be recruited with the aim to enroll 42 participants, 21 per group; for the cognitive and fMRI pilot studies, an additional 10 participants will be recruited with the aim to enroll 5 participants in the cognitive pilot and 5 participants in the fMRI pilot. Thus, this totals 94 participants (84 + 5 + 5 = 94) required to complete the cognitive pilot, fMRI pilot, and exercise training program/study intervention.

For the exercise training program/study intervention, the sample size for enrollment was determined from simulation-based power predictions for fMRI (Desmond & Glover, 2002), and based on a metaanalysis on exercise training effects on cognition in older adults (Colcombe and Kramer, 2003). 1) fMRI: Given an estimated mean difference of 0.5% signal change, a between-subject variance of 0.5%, and a statistical power of 0.80, a sample size of 11-12 subject per group would be needed for $\alpha = 0.05$ and N = 21 per group for $\alpha = 0.002$. 2) Cognition: we performed sample size calculations with G*Power 3.1.7 based on effect sizes reported in the literature. Effect sizes were f = 0.26 for a short-duration exercise intervention, f = 0.30 for session durations of 45 min, f = 0.20 for cardiovascular training only, f = 0.21 for the visuospatial domain, and f = 0.35 for participants aged 65+ years. Based on an average f of 0.26, a statistical power of 0.80, and alpha = 0.05, a total N = 32 subjects will be needed. Oversampling to 42

Risks and Benefits

Risks associated with the cardiovascular fitness and strength tests

The exercise test will require a gradual increase of exercise intensity. Because it is very strenuous to reach maximum oxygen uptake even after rest it may pose a health risk for some participants. Risks and discomforts include the possibility of adverse changes during the test, including abnormal blood pressure, fainting, dizziness, severe fatigue, body aches, heart rhythm abnormalities, stroke, and very rare instances of heart attack.

Risks and discomforts associated with the strength tests include feeling tired and experiencing muscle cramps. Other, less common, risks and discomforts include muscle tear, spraining a ligament (connective tissue) and lightheadedness.

Risks associated with bioelectrical impedance analysis (BIA)

The bioelectric impedance analysis (BIA) uses a very small electrical current, which passes between electrodes placed on the hands and/or feet. The amount of this current is slight enough that the participants will not be able to feel it and poses no risk to humans. However, there is a slight risk that this low current could disrupt an artificial pacemaker or defibrillator.

Risks associated with exercise

Walking and moderate-intensity physical activities are associated with a very low risk of musculoskeletal complications, but jogging and running are associated with increased risk of injury to the muscles, bones or joints. Acute heart attacks and sudden cardiac death can be triggered by unaccustomed vigorous physical exertion, particularly in sedentary men and women who have signs or symptoms of heart disease.

MRI risks

The MRI uses a strong magnet. The magnet may affect pacemakers, artificial limbs, and other medical devices that contain iron. The magnet will stop a watch that is close to the magnet. Any loose metal object has the risk of causing damage or injury if it is pulled toward the strong magnet. The loud acoustic noise from the MRI machine may cause hearing damage. Participants may also experience claustrophobia (fear of small spaces) or anxiety while in the magnet, because the top and sides of the machine will be very close to the body. There is a chance that the person performing the MRI may notice an incidental finding. It is possible that participants will be unnecessarily worried about the incidental findings.

Risks of completing tasks

Participants may get tired during the cognitive tasks.

Questionnaire risks

Participants may feel emotional or upset when answering some of the questions.

Loss of confidentiality

The main risk of using and storing identifiable information for research is a potential loss of confidentiality.

How risks will be

Risks associated with the cardiovascular fitness and strength tests

Because it is very strenuous to reach maximum oxygen uptake even after rest, and thus, may pose a health risk for some participants, we will estimate, rather than measure, the level of maximum oxygen uptake. Therefore, participants will perform a submaximal, incremental fitness test. This test will follow established standards of the American College of Sports Medicine (ACSM). We will instruct participants to let the technician know about any discomfort, such as dizziness, nausea, extreme shortness of breath, and extreme leg fatigue. Participants may ask to stop the test at any time. The staff members who will perform the fitness testing have current certification in cardiopulmonary resuscitation (CPR). We will ask participants not to engage in strenuous physical activity for 24 hours prior to the test. Participants are advised not to participate in the fitness assessment if they have any heart or lung conditions or symptoms, or if they have any physical impairment that would preclude them from performing the test safely. We will screen them for these conditions and symptoms prior to testing. During the tests we will monitor heart rate, blood pressure and perceived exertion. Only well-trained personnel (technicians, physiologists, nurses or physicians) will conduct the exercise test.

To reduce the risks associated with strength testing, participants will perform wrap-up exercises, and trained individuals will instruct them in proper technique. Participants will be able to take breaks as

Risks associated with bioelectrical impedance analysis (BIA)

We will exclude participants with pacemakers and defibrillators from participating in this study.

Risks associated with exercise

To reduce the risk of musculoskeletal injury and complications associated with exercise, the exercise training program will be tailored to each participant's ability level and supervised by an experienced

trainer. The trainer will instruct each participant in proper technique. To reduce injury risk, each exercise session will include a light cardiovascular warm-up, cool-down and stretching, and the amount and intensity of the exercise will gradually increase over the 12 weeks of the exercise training program.

MRI risks

Participants will be excluded if they have any metal in or on their body, regardless of whether the metal is ferromagnetic, if the metal cannot be removed. This includes implanted devices, such as pacemakers and defibrillators. Participants will be screened for claustrophobia (fear of small spaces). If participants feel anxious during the procedure, they can ask us to stop the MRI at any time. The MR technologist of the Cognitive Neuroimaging Center, who is trained in magnet safety, will prepare the participants for MR imaging and will perform the scans. To prevent potential hearing damage participants will be required to wear earplugs. The MR technologist and the study staff are trained in magnet safety and will communicate with the participant during the MRI session.

It is explained to the participants that the MRI scan being done is designed to answer research questions only and does not serve as a medical scan. However, if we believe that we have found a medical problem (or serious medical problem) in the MRI scan, we will consult the director of the Cognitive Neuroimaging Center, [name], D. Phil., and/or the center's MRI technologist, if needed. If [name], D.Phil., and/or the MRI technologist thinks that there may be an abnormality, we will contact the participant and will help them get medical follow-up for the problem. The MRI scan will not be reviewed by a clinically-trained physician as a part of this research study. With the participant's permission, we may contact their primary care physician.

Risks of completing tasks

The testing procedures include breaks and the participants can rest at any time, except during timed tasks. For tasks performed in the fMRI scanner, we will split the tasks into several runs with brief breaks between runs.

Questionnaire risks

Participants will be instructed to let the interviewer know at any time if they want to take a break or stop the interview. Participants are not required to answer any questions that make them feel uncomfortable. However, they may be excluded if it cannot be established whether or not the participant meets the inclusion and/or exclusion criteria.

Loss of confidentiality

We will protect each participant's confidentiality by labeling identifiable information with a code and keeping the key to the code separately from the research data either in a password-protected computer or as a paper file in a locked file cabinet. The master code is limited to BUMC investigators and we will not release it to anyone outside the institution. [name] will have access to the names and birthdates of participants in addition to the research data. Information will be stored on secure servers using REDcap or similar software. If it is necessary to use a laptop's hard drive for storage of identifiable information this laptop's hard drive will be encrypted with Truecrypt or similar disk encryption software prior to storing this information. All research staff will receive training in human subject protection and the HIPAA rule.

Potential Benefits

Benefits to subjects

Participants may or may not benefit from taking part in this study. Possible benefits to subjects include improved cardiovascular health, physical fitness and/or strength, and weight loss from participating regularly in the exercise training program.

Benefits to society

Others may benefit in the future from the information that is learned in this study. These potential benefits may include improved brain function through exercise and knowledge about how exercise affects the brain and cognitive (thinking) processes.

Risk to Benefit Ratio

Assessment of Risk/Benefit Ratio

Even though the exercise interventions, exercise testing and MRI procedures performed are solely done to answer research questions, the risks are very reasonable in relation to anticipated benefits. This is so, because the risks associated with the research study are only minimal, while the anticipated benefits to subjects are expected to be more than minimal due to the well-known health-related benefits associated with regular exercise.

Selected References

- Altman, J., & Das, G. D. (1965). Autoradiographic and histological evidence of postnatal hippocampal neurogenesis in rats. *Journal of Comparative Neurology*, 124(3), 319–335. https://doi.org/10.1002/CNE.901240303

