In line with new guidelines from the American College of Sports Medicine (ACSM), we will exclude participants if they have any known cardiovascular, pulmonary, or renal disease. Those who do not have any signs or symptoms, nor diagnosis, will not require medical clearance. This is also in line with new regulations from ACSM based on studies finding low predictability of adverse event by CVD risk factors, coupled with high prevalence in older adults. Only those older adults interested in participating in the research study that have any signs or symptoms of cardiovascular, pulmonary, or renal disease or mild musculoskeletal issues (such as osteopenia, osteoporosis, or arthritis) will be required to submit a medical clearance form signed by his or her physician before participating in exercise testing or training (FitRec Personal Training Medical Waiver form). In addition, we will exclude participants if they have any contraindicator of MR imaging (e.g. non-removable ferromagnetic metal in or on the body), bioelectrical impedance analysis (BIA; e.g. pacemaker), or if they have any neurological or psychiatric conditions or disorders that are known to affect the brain and cognitive functions. In addition, participants will be excluded if they are physically active, or are not considered "sedentary": The American College of Sports Medicine defines a sedentary lifestyle as a lifestyle in which a person is not participating in at least 30 minutes of moderate intensity physical activity on at least three days per week for at least three months (definition according to American College of Sports Medicine, Thompson et al., 2010). Finally, individuals will be excluded if they self-report susceptibility to severe motion sickness or claustrophobia, given that (1) the cognitive task performed in the MRI scanner may cause discomfort for individuals who are susceptible to motion sickness, and (2) being inside the MRI scanner may cause discomfort for individuals who are susceptible to claustrophobia.

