2. Body composition analysis using the InBody Test (approx. duration: less than 15 min) The InBody Test uses safe, low-level currents sent through the body via hand and foot electrodes. (The participant contacts these electrodes by standing on the device, which resembles a scale, and holding the cylindrical hand-held electrodes.) The impedance that the currents encounter are measured, and from there, body composition is derived. The amount of this current is slight enough that the participant cannot feel it. The InBody Test will provide an estimate of total body water, dry lean mass, body fat mass, weight, skeletal muscle mass, body mass index, and percent body fat. These estimates are printed out on the

InBody Results Sheet, which has been included with this protocol (InBody_E_Book.pdf). Each participant will be offered a copy of his or her results to compare body composition from before and after the exercise intervention. Outcome measures for the purposes of this study include weight, body mass index, and percent body fat.

3. Cardio-respiratory fitness tests (incremental work rate test) (approx. duration: 30-40 min) We will use standard submaximal clinical exercise testing procedures, including that of a submaximal, incremental work rate test, designed to ensure participant safety and measurement accuracy (Cooper and Storer, 2001; Thompson et al., 2010). We will follow the guidelines established by the American College of Sports Medicine for submaximal clinical exercise testing (ACSM; Thompson et al., 2010).

We will use a modified Balke treadmill protocol that uses a fixed walking speed and increasing increments in grade. We will choose the speeds and grades used for each participant (Cooper and Storer, 2001) so that all participants walk at a relatively comfortable pace with the grade increments calculated to provide a total test duration of 8-12 minutes (Buchfuhrer, 1983). The test will be continued until the participant reaches 85% of his or her age-predicted maximum heart rate (HRmax = 206.9 - (0.67 × age)) or 70% of heart rate reserve (HRreserve = HRmax –HRrest). While this test does not allow direct measurement of maximum oxygen uptake (VO2max),

the results of this test allow us to predict VO2max based on the known linear relationship between heart rate and VO2max. VO2max is a secondary outcome measure. Notably, participants will warm up for 3 to 4 minutes and cool down for 7 to 10 minutes before and after the test, respectively.

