For this test, participants will wear a chest strap to measure heart rate and a blood pressure cuff to measure blood pressure (BP). During the test, heart rate will be continuously monitored and recorded and BP will be measured at multiple points before, during, and after the test. We will take the participant's BP at standing rest on the treadmill, at the end of the 3-minute warm-up, and after completing the first 3 minutes of the test. If the participant demonstrates any adverse response to the exercise (e.g., demonstrating a BP over 220/110), we will continue to measure BP every 3 minutes during the test. If not, we will take BP immediately after the participant reaches 85% of his or her age-predicted maximal heart rate while treadmill speed and grade are quickly returned to low warm-up levels.

At regular intervals while performing the test, we will also ask the participant to rate how hard he or she believes he or she is exercising (using the standard 15-grade scale for ratings of perceived exertion; Borg, 1982, Table 1; see attached RPE scale). If the participant fails to conform to the exercise testing protocol, experiences adverse signs or symptoms, requests to stop, or experiences an emergency situation, we will terminate the test. Symptoms such as unusual shortness of breath or leg, back, or chest discomfort will be investigated, and the test will be stopped for participant safety. We will instruct the participant to inform the technician about any discomfort he or she experiences during the test, such as dizziness, nausea, extreme shortness of breath, and/or extreme leg fatigue. Participants may ask to stop the test at any time. Trained medical staff will be available or on call for each test.

Finally, following completion of testing, there will be a recovery time including a cool-down walk on the treadmill and sitting in a chair. Throughout the duration of the recovery time, heart rate and BP will be monitored until the participant's heart rate and BP have approximately returned to pre-exercise

baseline and/or until BP is below 140/90. (Notably, as per the expertise of our study exercise physiologist, exercise induced hypertension up to 220/110 during exercise is normal.

Thus, monitoring BP to a point where it is below 140/90 ensures that the participant's cardiovascular system is returning to normal levels.)

4. Strength Assessment (duration: approx. 30 min)

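### Treadmill test: with no adverse response, no blood pressure reading is scheduled between minute 3 and the end, so the plan's own 220/110 trigger is checked only once during graded exercise (minor safety point, cheap to improve)

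*Combined protocol and SAP*

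**What the plan says.** The schedule is in the combined protocol and SAP, Study Visit 2, item 3 (Cardio-respiratory fitness tests). Study Visit 40 repeats the Visit 2 procedures.

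- **Length.** Grade increments are chosen to "provide a total test duration of 8-12 minutes". Warm-up and cool-down lie outside that time: "participants will warm up for 3 to 4 minutes and cool down for 7 to 10 minutes before and after the test, respectively".
- **Fixed readings.** BP is taken at standing rest, at the end of warm-up, and "after completing the first 3 minutes of the test".
- **After an adverse response.** The example given is a participant "demonstrating a BP over 220/110), we will continue to measure BP every 3 minutes during the test".
- **With no adverse response.** "If not, we will take BP immediately after the participant reaches 85% of his or her age-predicted maximal heart rate", while speed and grade are being brought back to warm-up level.
- **Recovery.** "Throughout the duration of the recovery time, heart rate and BP will be monitored", until it has settled.

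The same item makes heart rate the only continuous measurement. Exertion is rated at intervals, participants report discomfort, and the test is terminated for adverse signs or symptoms. It also records the exercise physiologist's view that pressures up to 220/110 are normal during exercise.

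**The concern.** The protocol uses a BP value as its example of what should start closer monitoring. After minute 3, however, a participant who feels well and shows no other sign has no scheduled reading that could reveal that value. Because grade keeps rising, minute 3 is an early, low-workload point. The trigger is therefore checked once in the graded stage, at the point where it is least likely to be met, and not again while the load climbs.

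What is at stake is how soon the test staff learn of a raised pressure. If they learn of it during the test, they can still decide whether to stop. If they learn of it at the end reading, graded exercise is already over. The population makes this worth a look: participants are sedentary older adults, those without signs, symptoms or a diagnosis need no medical clearance, and the risk section lists abnormal blood pressure among the possible adverse changes during testing.

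**Working it through.** The documents state no gap length, so there is no figure of theirs to reproduce. The check is arithmetic on the schedule.

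**Inputs.** Planned test length T = 8 to 12 minutes; last fixed reading within the test at minute 3; next reading at the end if there is no adverse response (all from Study Visit 2, item 3). The enrolment target is 42 (Sample Size Justification), with one test at each of Visits 2 and 40.

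**Formulas.**
- Gap now = T − 3.
- With readings at minutes 3, 6, 9 and the end, the longest gap is 3 minutes.
- Worst-case delay for a rise that starts just after minute 3: T − 3 now, 3 with the change. Gain = (T − 3) − 3 = T − 6.

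| T (min) | Gap now (min) | Readings added at minute | Longest gap after (min) | Earlier detection (min) |
|---|---|---|---|---|
| 8 | 5 | 6 | 3 | 2 |
| 9 | 6 | 6 | 3 | 3 |
| 10 | 7 | 6, 9 | 3 | 4 |
| 11 | 8 | 6, 9 | 3 | 5 |
| 12 | 9 | 6, 9 | 3 | 6 |

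The last column is the largest gain. A rise that starts after the last added reading is found at the end reading either way.

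**Alternative reading of the test length.** If the 8-12 minutes included a 3-4 minute warm-up, the gap would run from 8 − 4 − 3 = 1 to 12 − 3 − 3 = 6 minutes. The protocol puts the warm-up before the test, so 5-9 minutes is the reading the text supports.

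**Other text.** Item 3 says in general terms that BP is taken at several points, and the risk-reduction section says it is monitored during testing. Neither gives a time between minute 3 and the end, so neither closes the gap.

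**Cost.** 42 × 2 = 84 tests if all participants complete; 84 × 1 = 84 to 84 × 2 = 168 extra readings.

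**The case against.** The schedule is deliberate. It has two clear branches, nothing in it is contradictory, and the test is submaximal under a stated commitment to ACSM guidelines. The end reading is close to peak workload, so a rise that lasts will be seen there. Screening lowers the risk: "we will exclude participants if they have any known cardiovascular, pulmonary, or renal disease", and signs or symptoms require physician clearance. During the test there are continuous heart rate, exertion ratings, symptom-based stopping, and medical staff available or on call. The gain in detection time is 2-6 minutes, less than the 5-9 minute gap suggests. Finally, more readings achieve little unless someone acts on them: the stated consequence of exceeding 220/110 is to start 3-minute readings, which would mean nothing if everyone already had them.

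Most of this stands as a limit on size, and the last point shapes the fix. It does not remove the gap. None of the listed safeguards measures BP between minute 3 and the end, and a general commitment to a guideline schedules no reading.

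A reader might infer that the schedule departs from the ACSM standard. The documents do not reproduce that standard, so this cannot be judged from them.

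A reader might also infer that some participants get no end reading, because the test may stop at 85% of maximum heart rate "or 70% of heart rate reserve" while the end reading names only the former. Taking the reserve target as resting rate plus 70% of reserve, the difference between the targets is 0.15 × HRmax − 0.30 × HRrest. Over assumed ages 60-80 and resting rates 60-80 bpm, the reserve target lies between 7 bpm earlier (0.15 × 166.7 − 0.30 × 60) and 1 bpm later (0.15 × 153.3 − 0.30 × 80). BP monitoring in recovery follows in any case. This is a matter of wording and not part of the point.

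**Conclusion.** The point holds as a minor safety improvement. With no adverse response, the longest interval without a scheduled BP reading in the graded test is 5 to 9 minutes, and the 220/110 trigger is checked only once in that stage. Reading every 3 minutes brings the interval to 3 minutes and detects a rise that starts just after minute 3 by 2 minutes (8-minute test) to 6 minutes (12-minute test) sooner.

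These figures rest on the planned 8-12 minutes. The test actually stops on heart rate, so individual intervals may differ. They concern only a rise with no symptoms or other adverse signs, since any adverse response already brings closer readings.

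Two stronger readings are not supported. A reader might infer that a high pressure would go unseen; the end and recovery readings would show a rise that persists, so the issue is mainly delay. A reader might also infer that the fitness results or the trial comparison are at risk. The predicted VO2max is based on heart rate, both arms follow the same procedure, and no outcome or group comparison depends on these readings.

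**What to change.** At Visits 2 and 40:

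1. Measure BP every 3 minutes during the graded test in all participants, whether or not an adverse response has occurred.
2. State that a reading over 220/110 prompts immediate review by the test staff, who decide whether to stop under the existing rule to terminate for adverse signs. This replaces the present consequence, which would no longer have any effect.

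The cost is about two sentences of protocol text and one extra cuff reading in an 8-9 minute test or two in a 10-12 minute test. The cuff is already worn and staff are present. The downside is slight discomfort while walking. Design, sample size and analysis are unchanged.

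As an optional clarification in the same edit, tie the end reading to whichever heart-rate end point stops the test.
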